9.2 Protocol for AE/SAE Data Collection and Reporting

All adverse events, unanticipated problems and potential risks will be monitored and collected ongoing and throughout the study by the study PI, research coordinator and research assistants. Events related to any patient and caregiver loss of privacy or confidentiality or discomfort, anxiety or distress related to completing the intervention or the outcome questionnaires will be assessed by the research assistant via monitoring of the BPSD and caregiver distress data reported by the caregiver via smartphone, by phone or face-to-face interactions and by patient and caregiver reports.

For all participants, **adverse events** will be collected starting at enrollment and continue until after the participant has completed the study. If an adverse event occurs, it will be documented on the NIA adverse event and serious adverse event forms found at:

<https://www.nia.nih.gov/research/dqcg/clinical-research-study-investigators-toolbox/adverse-events>.

Unanticipated problems that do not meet the definition of an adverse event, will be documented in a study log that will be stored in a secure electronic folder behind the IU fire wall. Details in the log may include participant study ID, date that the problem was reported or discovered by the study, a description of the problem, and a corrective plan and measures to prevent reoccurrence.

Measurement and Reporting of Adverse Events - Adverse events associated with monitoring of BPSD or caregiver distress related to AD are infrequent. Therefore, adverse event rates are expected to vary little between the two screening groups and control group. Adverse events will be monitored by the research coordinator on an ongoing basis. All adverse events and unanticipated problems will be reported to the study PI within 24 hours. We plan to present adverse events data to the DSMP safety officer when requested and at scheduled meetings. The NIA adverse event form will be used by the study staff to report all adverse events caused by the intervention.

In the case of a participant death related to the intervention, the NIA Program Officer, the IU IRB and the Safety Officer will be notified within 24 hours using NIA standardized forms for reporting serious adverse events (noted above). If unanticipated, serious adverse events occur (i.e., not listed in the Data and Safety Monitoring Plan) and that are related to the intervention, they will be reported to NIA Program Officer, the IU IRB, and to the study Safety Officer within 48 hours of study's knowledge of the event using NIA standardized forms for reporting serious adverse events. In cases where there is any question regarding the level of an adverse event or attributable cause, or areas of uncertainty, the study team and PI will consult with the Safety Officer and IU IRB. The summary of all other adverse events and unanticipated problems should be reported to NIA Program Officer and to the Safety Officer **semi-annually**, unless otherwise requested.

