- **Not Related**: - The adverse event is clearly not related to the investigational agent/procedure - i.e. another cause of the event is most plausible; and/or a clinically plausible temporal sequence is inconsistent with the onset of the event and the study intervention and/or a causal relationship is considered biologically implausible.

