10.7 Stopping Rules

To ensure the integrity of the data, our study biostatistician will perform monthly cross tabulations of the data to confirm that each data field is being filled properly. It is unlikely that the study would be stopped early due to important favorable differences in the intervention group compared to control group because of the nature of the intervention and outcome measures. However, the study could be stopped early due to adverse events. Some events of particular concern would be a high number of study withdrawals due to discontent with the study procedures. The IU IRB and/or NIA Program Officer will make the final decision on whether or not to accept the Safety Officer's recommendation about discontinuation of any component of the study.

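### Section 9.2 gives two unreconciled scopes for the adverse-event form, and app-based detection exists in one arm only, so between-arm adverse-event rates are open to ascertainment bias

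*Combined protocol and SAP*

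**What the plan says.** **Scope of collection.** Section 9.2 opens widely: "All adverse events, unanticipated problems and potential risks will be monitored and collected ongoing and throughout the study". For every participant, adverse events "will be collected starting at enrollment and continue until after the participant has completed the study". The recording rule that follows has no condition on cause: "If an adverse event occurs, it will be documented on the NIA adverse event and serious adverse event forms found at" an NIA web page.

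**Second statement about the form.** Further on in 9.2, the paragraph on measurement and reporting ends: "The NIA adverse event form will be used by the study staff to report all adverse events caused by the intervention".

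**Detection.** For loss of privacy, and for distress from the intervention or the outcome questionnaires, the research assistant assesses events "via monitoring of the BPSD and caregiver distress data reported by the caregiver via smartphone, by phone or face-to-face interactions", and also through patient and caregiver reports.

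**Relatedness.** Under 9.1.1 the PI judges relatedness, with coordinator input, against the intervention and/or participation. One category begins: "The adverse event is clearly not related to the investigational agent/procedure".

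**Use.** Section 9.2 states that "adverse event rates are expected to vary little between the two screening groups and control group". Sections 10.1 and 10.6 list adverse event rates among the items reported to the Safety Officer. Section 10.7 says: "However, the study could be stopped early due to adverse events". Section 12.5 reviews adverse events once 77 dyads have completed.

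**Schedule.** Table 4 has no adverse-event item at any visit. It does list EMR data at baseline, 3 and 6 months, with no restriction by arm.

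**The concern.** There are two separate problems, and they compound.

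First, staff have two instructions for one form. Someone following the second would have to decide whether the intervention caused an event before filling in the form. That would pre-empt the PI's relatedness assessment in 9.1.1 and leave little use for its unrelated category.

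Second, even if every detected event is recorded, the arms are not observed equally. App records and the calls they trigger arise only in the intervention arm. No common adverse-event question at the visits offsets this. Patients attend no research visit (Section 7.0), so their events surface largely through contact with the caregiver, and that contact is what differs.

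At stake is how the safety reports are read. An apparent excess in the app arm could reflect more contact rather than more harm. A reassuring similarity could hide a real difference if events were filtered by cause beforehand.

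**Working it through.** The plan states no adverse-event rate, count or boundary, so there is no figure to reproduce. The check has three steps.

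**1. The two statements on the form, side by side.**
- Statement A (any adverse event, all participants): record first, classify afterwards. The unrelated category in 9.1.1 has a purpose only under A.
- Statement B (events caused by the intervention): it is silent on other events and does not say *only*. It agrees with A if it concerns onward reporting. It conflicts with A if it governs when a form is completed.
- The reporting sections lean towards A, but not uniformly. Section 9.2 sends a semi-annual summary of all other adverse events and unanticipated problems, and 10.2(a) requires an adverse-event summary with no limit by cause. In 10.1, the matching sentence covers all other *serious* adverse events.

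The text therefore does not settle which rule staff should follow.

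**2. Scheduled contacts by arm.**
- Inputs: six one-month periods alternating weekly and monthly (Section 5.0, Section 6.4, Table 1), so three of each whichever comes first; visits at baseline, 3 and 6 months in both arms; no app in controls (Section 5.0).
- App NPI-Qs: 3 × 4 + 3 × 1 = 15 (3 × 30/7 + 3 = 15.9 if 30-day periods are counted exactly).
- After baseline: intervention 15 + 2 = 17, control 2. With baseline: 18 versus 3, a ratio of 18/3 = 6.
- Triggered calls come on top. Under Section 7.0 a threshold crossing at a visit leads to a call in either arm; a crossing in the app can do so only in the intervention arm. The documents do not give the number of calls.

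**3. What unequal capture could do (illustration only).** Let the true risk p be equal in both arms, with 77 dyads per arm and capture proportions c_I (intervention) and c_C (control). Expected recorded dyads are 77 × p × c in each arm, and the ratio is c_I / c_C whatever p is. With p assumed to be 20%:
- Full capture in both arms: 77 × 0.20 = 15.4 versus 15.4, ratio 1.
- c_I = 95%, c_C = 80%: 77 × 0.20 × 0.95 = 14.6 versus 77 × 0.20 × 0.80 = 12.3, ratio 1.19.
- c_I = 95%, c_C = 50%: 14.6 versus 77 × 0.20 × 0.50 = 7.7, ratio 1.9.

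The values of p, c_I and c_C are all assumptions. The figures show the direction and a possible range, not an estimate.

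**The case against.** The strongest reply is that 9.2 as a whole is inclusive. It collects all adverse events for all participants, sends them to the PI within 24 hours, and provides an unrestricted semi-annual summary. The form sentence does not say *only* and may describe onward reporting. Phone contact, face-to-face contact, spontaneous reports and the three visits are common to both arms. The smartphone source is named for privacy and distress events, not for deaths or admissions. Adverse events are expected to be infrequent, and no between-arm test is planned.

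Most of this stands, and it rules out several stronger readings that a reader might infer:
- *That controls can have no reportable event.* Relatedness in 9.1.1 extends to participation, and 9.2 counts distress from the outcome questionnaires, which controls also complete.
- *That the Safety Officer would see an intervention-only list.* The summaries in 9.2 and 10.2(a) are not limited by cause.
- *That the coordinator decides causation.* Section 9.1.1 gives that judgement to the PI.
- *That 10.7 sets a stopping rule on between-arm rates.* It allows stopping for adverse events, and its own example is withdrawals due to discontent with study procedures.
- *That the contact counts convert into detection probabilities.* Doing so would treat an app questionnaire as equal to a visit, assume independent contacts, and ignore triggered calls and spontaneous reports.

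The reply does not reconcile the two form sentences, and it does not supply a detection source that is applied identically in both arms.

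**Conclusion.** The point holds in a limited form. Section 9.2 needs one rule on which events go on the form. Between-arm adverse-event rates are open to ascertainment bias because about 15 app questionnaires, and any calls they trigger, exist in one arm only. The rates can still be compared; the comparison would be descriptive and could be biased. The likely direction is towards more recorded events in the intervention arm, mainly among distress and privacy events, for which the smartphone source is named. The documents give no capture rate, so the size is unknown; the assumed range above gives ratios of 1.19 to 1.9 with no true difference. The effect falls on safety monitoring and on the statement that rates will differ little between groups. It does not affect the efficacy analyses. The change is worth making because it is cheap and brings the form rule into line with the collection scope that 9.2 already sets.

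**What to change.** 1. In 9.2, delete the last four words of "The NIA adverse event form will be used by the study staff to report all adverse events caused by the intervention", so that every adverse event in either dyad member, in both arms, is recorded first and then classified for relatedness by the PI.
2. Add one row to Table 4: an identical adverse-event question put to caregivers in both arms at the 3- and 6-month visits, covering both dyad members.
3. Use the EMR data already scheduled at those visits to identify patient deaths, hospitalisations and emergency visits. This serves patients only, because Table 3 lists no EMR data for caregivers; caregiver events depend on item 2.
4. Report between-arm rates from these common sources, and list app-detected events separately.
5. Align the semi-annual summary wording in 9.2 and 10.1.

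The cost is a wording change, one schedule row and some additional extraction from a record review already planned. The downside is more forms, mostly for events judged unrelated.

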10.0 Data Safety Monitoring

The data safety monitoring plan (DSMP) for this trial will be monitored by the PI and a Safety Officer from an outside institution. The Safety Officer will act in an advisory capacity to the IU IRB and NIA Program Officer to monitor participant safety, evaluate the progress of the study, to review procedures for maintaining the confidentiality of data, the quality of data collection, management, and analyses.

10.1 Frequency of Data and Safety Monitoring

The Safety Officer and the PI will meet by teleconference initially to review and approve the study protocol and DSMP. Following that initial meeting, the Safety Officer and the PI will meet twice annually, either in person or by teleconference, to review study progress, data quality, and participants' safety. The first DSMP review will occur six months after approval to begin recruitment. Reporting will include subject accrual, adverse event rates, subject complaints, compliance to interventions, and protocol violations/noncompliance. Thereafter, the PI and Safety Officer review will occur every six months and review of adverse events reports will occur as summarized in table 5.

Table 5. Safety Officer Reporting

Frequency of Review			
	Each Occurrence	Quarterly	Semi-Annually
Subject accrual (adherence to inclusion/exclusion); drop-out rates; randomization		X	X
Serious adverse events (e.g. death)	X	X	X
Adverse events		X	X
Subject Complaints		X	X
Compliance with Intervention		X	X
Protocol Violation/Non-compliance		X	X
Stopping rules report	X		X

The PI is responsible for collecting and recording all study data and ensuring participants safety on a daily basis. Adverse events, will be monitored on an ongoing basis by the study research assistant and PI. All adverse events and unanticipated problems will be reported to the study PI within 24 hours. In the case of a participant death related to the intervention, the NIA Program Officer, the IU IRB and the Safety Officer will be notified within 24 hours. If unanticipated, serious adverse events occur (i.e., not listed in the Data and Safety Monitoring Plan) and that are related to the intervention, they will be reported to NIA Program Officer, the IU IRB, and to the Safety Officer within 48 hours of study's knowledge of the unanticipated serious adverse event. In cases where there is any question regarding the level of an adverse event or attributable cause, or areas of uncertainty, the study team will consult with the Safety Officer and IU IRB. The summary of all other serious adverse events should be reported to NIA Program Officer and to the Safety Officer semi-annually, unless otherwise requested by the Safety Officer.

10.2 Content of Data and Safety Monitoring Report

The research coordinator and study biostatistician will generate data and safety monitoring reports for PI and the Safety Officer that will contain:

- a) Summary of adverse events and an explanation of how each event was handled,
- b) Summary of complaints and how each complaint was handled,
- c) Subject retention, including the number and reasons of participant withdrawals, and study quality
- d) Intervention compliance (session attendance), and
- e) Summary of protocol violations and how each was handled. All reports will be submitted to IU IRB at time of continuing review.

10.3 Safety Officer Affiliation

The Safety Officer will be determined after the NIA review of the proposed study DSMP. The Safety Officer will be reviewed and approved by the NIA. Should there be any questions regarding the independence of the Safety Officer, they will be addressed and corrected if necessary at that time.

10.4 Conflict of Interest for Safety Officer

The Safety Officer will not have a direct involvement with the study or conflict of interest with the investigators or institutions conducting the study. The Safety Officer will complete COI forms that report all financial interests such as salary, consulting and / or speaker fees, honoraria, research support, equity interests (e.g., stocks, stock options, or other ownership interests), and intellectual property rights (e.g., patents, copyright and royalties from such rights).

10.5 Protection of Confidentiality

Data presented at the PI and the Safety Officer semiannual meeting, the Safety Officer Reports, and discussions at the meeting will be kept confidential. Participant identities will not be known to the Safety Officer

10.6 Safety Officer Responsibilities

In summary, the Safety Officer will meet with the PI by teleconference or in person, initially to review and approve the protocol and DSMP, and then will meet semi-annually to review study progress, data quality, and participants' safety. Reporting will include subject accrual, adverse event rates, subject complaints, compliance to interventions, and protocol violations/noncompliance. Other Safety Officer responsibilities include:

- Review the research protocol, informed consent documents, plans for data safety and monitoring, and Manual of Procedures;
- Recommend subject recruitment be initiated after receipt of a satisfactory protocol;
- Evaluate the progress of the trial, including periodic assessments of data quality and timeliness, recruitment, accrual and retention, participant risk versus benefit, performance of the trial sites, and other factors that can affect study outcome;
- Consider factors external to the study when relevant information becomes available, such as scientific or therapeutic developments that may have an impact on the safety of the participants or the ethics of the trial;
- Review study performance, make recommendations and assist in the resolution of problems reported by the Principal Investigator;
- Protect the safety of the study participants;
- Report to NIA on the safety and progress of the trial;
- Make recommendations to the NIA and the Principal Investigator concerning continuation, termination or other modifications of the trial based on the observed beneficial or adverse effects of the treatment under study;
- If appropriate, review data in accordance with stopping rules, which are clearly defined in advance of data analysis.
- Ensure the confidentiality of the study data and the results of monitoring; and,
- Assist the NIA by commenting on any problems with study conduct, enrollment, sample size, and/or data collection.

10.7 Stopping Rules

To ensure the integrity of the data, our study biostatistician will perform monthly cross tabulations of the data to confirm that each data field is being filled properly. It is unlikely that the study would be stopped early due to important favorable differences in the intervention group compared to control group because of the nature of the intervention and outcome measures. However, the study could be stopped early due to adverse events. Some events of particular concern would be a high number of study withdrawals due to discontent with the study procedures. The IU IRB and/or NIA Program Officer will make the final decision on whether or not to accept the Safety Officer's recommendation about discontinuation of any component of the study.

10.8 Limits of Assumptions

It is possible that baseline differences between the groups, excessive study dropouts and/or missing data by the interim measurement time point (midway point to targeted enrollment) will limit the value of data analysis of measurements. Baseline differences will be evaluated after the first measurement time point and effects on the power to detect differences in the primary outcome will be evaluated and communicated by the study biostatistician to the PI and Safety Officer. Given the monitoring plans outlined, it is exceedingly unlikely that there will be baseline differences between groups of any magnitude to threaten the validity of the study.

11.0 Study Withdrawal/Discontinuation

Participants can decide to withdraw from the study at any time. The study team will help the participant safely withdraw from the study.

To withdraw from the study the participant must either contact the principal investigator [name], MD by [contact] (voicemail) or in writing [contact] (email) or address: [name], IU Department of Psychiatry, [name]

If they cannot reach [name] during his regular business hours (i.e. 8:00AM-5:00PM), they can call the IU Human Subjects Office at [contact] or [contact].

There are no expected risks for early withdrawal from the study.

12.0 Statistical Considerations and Analysis

12.1 AIM 1: Quantitatively and qualitatively, determine the feasibility of collecting responses on an EMA version of the Neuropsychiatric Inventory Questionnaire (NPIQ-EMA) from caregivers using smartphone technology at differing frequency intervals weekly or monthly, or a control group with data collected without the mobile health version and only at baseline and 6 month).

H1: Caregivers in the intervention groups will complete the assessments via smartphone and report an acceptable response burden. We anticipate that the response burden will be comparable to data collected in routine office visits.

Analysis H1: The primary outcomes for AIM 1 are feasibility and usability.

Feasibility will be measured 5 different ways:

- 1) Completion rate of the NPIQ-EMA over 6 months
- 2) Answers to the NPIQ-EMA response burden question every time the NPIQ-EMA is completed: "How burdensome was completion of the prior scale (Answer options: not at all burdensome, mildly burdensome, moderately burdensome, or extremely burdensome)"
- 3) Completion rate of the semi-structured phone interviews triggered by "clinically significant" symptoms
- 4) Post-intervention survey (quantitative)
- 5) Post-intervention semi-structured interview (qualitative) occurring immediately at the end of 6 months.

Usability will be measured in 3 different ways post-intervention:

- 1) System usability scale (SUS) total score
- 2) Post-intervention survey (quantitative)
- 3) Semi-structured phone interview (qualitative).

Quantitative Analysis: For quantitative analyses, there scores are continuous scale scores. Therefore, the intervention group feasibility scores will be compared to the control group's feasibility (response burden question) relative using ANCOVA to adjust for baseline characteristics including baseline demographics. The adjustment for baseline will increase precision and will statistically ensure comparability of the baseline level symptoms, even though random assignment should generally provide approximate comparability across a host of baseline characteristics.

Qualitative Analysis: We will interpret the post-intervention semi-structured interview feasibility and usability questions with the thematic analysis methodology developed by Braun and Clarke⁴⁴. We will take an inductive approach searching for observed patterns and working to develop theories for these findings⁴⁴. Reflexivity journals, subjective reflections of the investigators interpretation of emerging findings, will be used to help account for differences in investigator biases, values and judgments^{45,46}. Expected outcomes regarding feasibility and usability will inform app development for AD caregivers in the future.

12.2 AIM 2: Determine whether more frequent surveillance of BPSD yields more actionable data.

H2: We expect there to be more occurrences of actionable data in the groups (i.e., intervention vs control) or conditions within a group (i.e., weekly vs monthly condition within the intervention group) that have more frequent monitoring.

Analysis H2: We define actionable data as data that could lead to a change in care plan. This was operationalized by setting “clinically significant” thresholds for NPI-Q symptoms and caregiver distress (see research design and methodology overview) that when reached led to contact and interval assessment between the research team and the caregiver. We will compare groups and conditions on the percentage of participants in each group or each condition that met at least one “clinically significant” threshold per month.

A between-group test, using mixed nonlinear models to adjust for baseline covariates, will be used to compare the intervention group to the control group. A within-group test, using mixed *nonlinear* models to adjust for baseline covariates as well as the period effect (i.e., months 1-6) and the randomized condition (i.e., assigned to start with weekly vs monthly surveillance frequency), will be used to compare the two surveillance conditions (measured weekly or monthly depending on the month period) within the intervention group in a 2 x 6 cross-over analysis.

12.3 AIM 3: Explore whether different surveillance intervals are associated with greater improvement in BPSD and CG distress.

H3: Groups or conditions within a group that receive more frequent surveillance paired with response to “clinically significant” symptoms will have greater improvement in BPSD and in caregiver distress.

Analysis H3: The change in rating of BPSD calculated by the difference in NPI-Q total scores and caregiver distress calculated by the difference in NPI-Q caregiver distress total scores at time of baseline assessment, 3 months and 6 months of the intervention group will be compared to the control group during the same time intervals. For this comparison we will use a between-group test, using mixed linear models to adjust for baseline covariates and to adjust for the baseline measure of the response variable (i.e., baseline NPI-Q total score or NPI-Q caregiver distress total score), will be used to compare the intervention group and control group on the repeated measured follow-up response variables (i.e., follow-up NPI-Q total score or NPI-Q caregiver distress total score). Separate models will be run for the NPI-Q total score and NPI-Q caregiver distress total score. A within-group test, using mixed *linear* models to adjust for baseline covariates and to adjust for the baseline measure of the response variable (i.e., baseline NPI-Q total score or NPI-Q caregiver distress total score) as well as the period effect (i.e., months 1-6) and the randomized condition (i.e., assigned to start with weekly vs monthly surveillance frequency), will be used to compare the two surveillance conditions (measured weekly or monthly depending on the month period) within the intervention group in a 2 x 6 cross-over analysis. We will also use these *linear* mixed models to perform the same type of between-group and within-group analyses in which the dependent variables are the following secondary variables: Perceived Stress Scale-14, and Zarit Burden Interview.

12.4 Power Justification and Analysis: The study was designed to have a power of 80% for two-tailed tests with a significance of 5%.

In the original power justification, we used a Cohen's d effect size of 0.65, which is between a medium (0.50) and a large (0.80) effect size. This was done primarily because of budgetary constraints associated with the K23 funding mechanism, which limited our ability to detect effect sizes smaller than 0.65 by enrolling beyond the proposed 96 dyads. However, with additional institutional funding support for 40% RA effort over 30 months we are now able to accommodate an enrollment sample size of 154 dyads (77 in each group), resulting in a projected 64 analyzable participants in each arm (control and intervention) after accounting for an attrition rate of 17% seen in the previously noted in the protocol trial (Callahan et al., 2006; Calculation = $(64 \times 2)/0.83 = 154$). The analyzable sample of 64 per arm for two-tailed tests of two independent populations will provide 80% power (using alpha = 0.05) to detect a medium effect size of 0.50, which is a common effect size chosen in both R01 and K-series proposals. The power for paired within-group tests between weekly vs monthly conditions for the 64 analyzable intervention participants will be slightly greater than 80% power. Selecting a medium effect size of 0.50 matches the effect size seen in the aforementioned non-pharmacologic protocol trial, where effect sizes for total NPI score and NPI caregiver distress score improvements at 12 months were 0.502 and 0.568, respectively (Callahan et al., 2006). We expect that this would require approaching 12 dyads per month and consenting and enrolling 6 dyads per month (1-2 dyads per week) over a span of 30 months.

The SECBCI practice employs 6 physicians each with a half day clinic where they see between 4 and 9 patients on any given half day. Meaning that a range of 24 – 54 total patients are seen per week, with over one third of patients carrying a diagnosis of AD, leading to projections of between 8 – 18 eligible patients per week. Our prior work has consistently shown a recruitment rate of 50% for eligible patients, meaning that it would be reasonable to expect a maximal consent and enrollment rate of 4 – 9 subjects per week, a number much greater than the required study recruitment number of 1 – 2 subjects per week.

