2.0 Objective(s)

AIM 1: Quantitatively and qualitatively, determine the feasibility of collecting responses on an ecological momentary assessment (EMA) version of the Neuropsychiatric Inventory Questionnaire (NPI-Q), via the Brain CareNotes Mobile Application (BCN), from caregivers randomly assigned to using smartphone technology at differing frequency intervals, compared with a control group with data collected without the mobile health version and only at baseline and 6 months). **H1:** Caregivers in the intervention groups will complete the assessments via smartphone and report an acceptable response burden.

AIM 2: Determine whether more frequent surveillance of BPSD yields more actionable data. **H2:** We expect there to be more occurrences of “actionable data” in the groups (i.e., intervention vs control) or conditions within a group (i.e., weekly vs monthly condition within the intervention group) that have more frequent monitoring. We define actionable data as data that could lead to a change in care plan. This was operationalized by setting “clinically significant” thresholds for NPI-Q symptoms

AIM 3: Explore whether different surveillance intervals are associated with greater improvement in BPSD and CG distress. **H3:** Groups or conditions within a group that receive more frequent surveillance paired with response to “clinically significant” symptoms will have greater improvement in BPSD and in caregiver distress.

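### H1 expects response burden to be acceptable and comparable to office visits, but the planned ANCOVA tests only for a difference between arms and can show neither

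*Combined protocol and SAP*

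**What the plan says.** Section 12.1 names feasibility and usability as the primary outcomes of Aim 1 and states H1: "Caregivers in the intervention groups will complete the assessments via smartphone and report an acceptable response burden". It then adds an expectation: "We anticipate that the response burden will be comparable to data collected in routine office visits". That sentence does not accompany H1 in sections 1.0 or 2.0.

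Burden is a single item with four ordered answers: "not at all burdensome, mildly burdensome, moderately burdensome, or extremely burdensome". Section 12.1 treats the scores as continuous and says that "the intervention group feasibility scores will be compared to the control group's feasibility (response burden question) relative using ANCOVA", with adjustment for baseline characteristics. Nowhere do the documents define acceptable, set a margin, or say which result would support or refute H1 on burden.

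Section 12.4 sizes the study for two-tailed tests at 5%, with 64 analysable dyads per arm and 80% power at a standardised difference of 0.50. It supports that effect size with NPI total and caregiver distress results from an earlier trial, not with data on response burden.

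The documents are not clear on who answers the burden item:
- Section 3.1.3 has it asked at every NPI-Q completion; section 12.1 says at every completion of the smartphone version.
- Section 7.0 describes it for intervention caregivers, after the app-delivered NPI-Q. None of its visit lists includes it.
- Table 4 lists it as a BCN app item at all three visits, flagged as triggered by clinically significant symptoms. It lacks the intervention-only note that the System Usability Scale and the post-intervention survey carry.
- Section 5.0 says that controls do not receive BCN.

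**The concern.** Acceptable and comparable both mean that burden is not too high. A difference test starts from no difference and asks whether the data contradict it. A non-significant result leaves comparability unproven, and becomes more likely as data grow fewer or noisier. A significant result would not show that burden is unacceptable either, since a small increase may still sit among the mild answers. The planned test therefore does not answer the question that H1 asks.

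The burden item is the only feasibility measure that section 12.1 names for the between-arm comparison. Section 16.2.1 lists added caregiver burden as a main worry, and section 1.0 says that the feasibility data will support a later grant application. A statement that burden was acceptable or comparable would carry weight there.

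**Working it through.** **Inputs.** From section 12.4: 64 analysable per arm, two-sided alpha 5%, standardised difference 0.50, attrition 17%, 154 enrolled. Assumed: burden differences in SD units, one value per caregiver, and an unadjusted t-test. The documents give neither an SD nor a margin for burden.

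**1. The plan's own figure.** n per arm = 2 × ((1.960 + 0.842)/0.50)² = 62.8, so 63 by the normal approximation; the t-test gives 63.8, so 64. Power at 64 per arm is 80.1% by the t-test. Enrolment: 128/0.83 = 154.2, against 154 stated. The figure reproduces.

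**2. Chance of a non-significant result.** One minus t-test power at 64 per arm:

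| True increase in burden | Non-significant |
|---|---|
| 0.2 SD | 80% |
| 0.3 SD | 61% |
| 0.4 SD | 39% |
| 0.5 SD | 20% |
| 0.65 SD | 5% |

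Covariate adjustment would lower these somewhat.

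**3. What a non-significant result leaves open.** The standard error is √(2/64) = 0.177 SD. The 95% half-width is 1.979 × 0.177 = 0.35 SD. An observed increase just under 0.35 SD is non-significant, and its upper 95% limit is 0.35 + 0.35 = 0.70 SD.

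**4. What a margin-based rule could deliver.** Non-inferiority at one-sided 2.5%, true difference 0: power = Φ(margin/0.177 − 1.960).

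| Assumed margin | Power at 64 per arm | n per arm for 80% |
|---|---|---|
| 0.5 SD | 81% | 63 |
| 0.4 SD | 62% | 99 |
| 0.3 SD | 40% | 175 |
| 0.2 SD | 20% | 393 |

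If comparable means two-sided equivalence (two one-sided tests at 5%), power at a 0.5 SD margin is 2Φ(2.828 − 1.645) − 1 = 76%.

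**5. What a single-arm rule could deliver.** With 64 intervention caregivers and an observed proportion p in the two lowest categories, the lower 95% limit is about p − 1.96 × √(p(1 − p)/64). For illustration:
- p = 70%: 0.70 − 1.96 × 0.057 = 59%
- p = 80%: 0.80 − 1.96 × 0.050 = 70%
- p = 90%: 0.90 − 1.96 × 0.0375 = 83%

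This needs no control data.

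**The case against.** The strongest reply is that H1 asks only for acceptable burden. Comparability is something the authors anticipate, in one sentence of section 12.1. This stands: H1 should not be recast as a formal non-inferiority hypothesis. But acceptable has no threshold either, so the missing criterion remains.

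A reader might infer that the plan will take a non-significant ANCOVA as proof of comparability. The documents do not say so; they do not say how such a result will be read. The gap is a missing rule, not a wrong one.

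A reader might also infer that clearly higher burden would go unnoticed. The figures do not support that: 0.5 SD is missed about 20% of the time and 0.65 SD about 5%. The weakness lies in small to moderate increases.

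Burden is also only one of five feasibility measures. Most of the others do not depend on the ANCOVA, and section 16.2.1 adds a burden check in the first 10 dyads. This limits the damage to Aim 1 as a whole but gives H1 no criterion on burden.

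Finally, controls may answer the item after all. Section 12.1 presumes it, and section 3.1.3 and Table 4 can be read that way. If they do, the ANCOVA already yields an adjusted difference with a confidence interval, and only a decision rule is missing. If they do not, the ANCOVA cannot be run and the between-arm figures above do not apply.

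**Conclusion.** The point holds in a limited form. Section 12.1 sets two expectations for burden, and its only inferential analysis can establish neither. At 64 per arm, true increases of 0.2 to 0.5 SD are non-significant in about 80% to 20% of trials, and a result just short of significance is compatible with an increase of about 0.7 SD. These figures assume control answers exist, an unadjusted comparison and SD units that the documents do not supply.

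Routine office visits, the stated comparator, are not measured: control data come from research visits by phone or on the hospital campus. Whether controls answer the burden item is unresolved.

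It would be too strong to say that the planned sample makes a proper test of comparability readily affordable. That is so only at an assumed margin of about 0.5 SD, the same size as the effect that section 12.4 calls medium. Any tighter margin is underpowered.

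**What to change.** In section 12.1:

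1. **Main rule, intervention arm only.** H1 on burden holds if the lower 95% confidence limit of the percentage of intervention caregivers answering 'not at all' or 'mildly' burdensome exceeds a level fixed before data are seen. State how each caregiver's repeated answers reduce to one value, and how caregivers with no answers are counted.
2. **Control data.** State whether control caregivers are asked the same item after their visit NPI-Q, and reconcile sections 3.1.3, 7.0, 12.1 and Table 4.
3. **If controls are asked,** name that visit NPI-Q as the comparator and report the ANCOVA-adjusted difference with its 95% confidence interval. Claim comparability only if the upper limit is below a pre-set margin expressed on the four-category item.
4. **If they are not,** drop the between-arm comparison and the comparability statement. In either case, remove the reference to routine office visits.

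The cost is SAP wording and the choice and justification of a level and, if used, a margin. The main rule needs no new data. The between-arm rule needs control answers, and the sponsor should accept in advance its power of about 80% at a 0.5 SD margin, 62% at 0.4 SD and 40% at 0.3 SD.
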